9.7. Sample Collection and Handling

The actual dates and times of sample collection must be recorded in the CRF or laboratory requisition form.

Refer to the [Time and Events Schedule](#) for the timing and frequency of all sample collections. For visits with study agent administration, all blood samples for assessing golimumab concentration and antibodies to golimumab must be collected before the administration of the study agent.

Instructions for the collection, handling, storage, and shipment of samples are found in the laboratory manual that will be provided. Collection, handling, storage, and shipment of samples must be under the specified, and where applicable, controlled temperature conditions as indicated in the laboratory manual.

9.8. Data to be Collected by Subjects

For this study subjects/caregivers will obtain and record a number of pieces of data to aid in endpoint analysis and compliance. The data will be collected using an eDiary that will be supplied by the sponsor to the subject/caregiver during the screening visit. Training on devices and what data is to be collected will be conducted by study-site staff at that visit, and at subsequent visits as needed. All data recorded in the eDiaries will be reviewed by study staff during study visits. For the open-label extension period, paper diaries instead of eDiaries will be provided.

- **Exogenous insulin administration.** Subjects/caregiver are to record the type and amount of insulin they have used during the 7-day period immediately preceding each study visit (see the [Time and Events Schedule](#)). This data will be used to calculate exogenous insulin use in units/kg/day. During the open-label extension period, subjects will be required to record 10 days of insulin use prior to each visit.
- **Hypoglycemic events.** Subjects/caregivers are to record information surrounding all BG measure measurement that are ≤ 70 mg/mL or of suspected hypoglycemia due to clinical symptomatology. Data including BG level, clinical symptoms (including but not limited to change in mental status or loss of consciousness), length of the event, therapies used to treat the event, and if assistance or medical care (including clinic, emergency room or hospitalization) was required for the event.
- **Study agent dosing.** For subjects/caregivers participating in self-administration they are to record study agent administration date, time, and anatomic location of the injection, person administering study agent, and if there are any complications associated with study agent administration.
- **Glucometer readings.**
 - Screening – Double-blind Week 104: Subjects/caregivers will be given a sponsor-supplied glucometer and supplies to self-monitor BG levels during the study. Subjects/caregivers may not use their own glucometers. Blood glucose readings should take place at least 4 times a day, ie, premeal and at bedtime, as needed and at any time of suspected hypoglycemia. Blood glucose readings from the provided glucometers will be electronically transmitted to the eDiaries provided or when BG levels ≤ 70 mg/mL during the double-blind period (Weeks 0 to 104).
 - Open-label Weeks 0 to 52: During this phase, subjects may use either fingersticks or continuous glucose monitoring (CGM) at the discretion of the investigator and/or according to local practice. The subjects will not be required to download BG values from the eDiary.

9.9. Injection Site Reaction Monitoring

Injection reactions or allergic reactions have been observed with administration of monoclonal antibodies. Mild to serious local and systemic reactions (including anaphylaxis) may occur at any time during the administration of study agent.

Study agent must not be administered to individuals with known or suspected intolerance or hypersensitivity to any biologic medication or known allergies or clinically significant reactions to human proteins, to monoclonal antibodies or antibody fragments, or to any components of golimumab or its excipients.

A physician must be immediately available at the site during the first 3 dose administrations of study agent for the double-blind period and open-label extension period. All subjects receiving study agent must be carefully observed for symptoms of an injection site reaction and a systemic reaction for at least 30 minutes after study agent administration.

Injection Site Reactions

An injection site reaction is any unfavorable or unintended sign that occurs at the study agent injection site. If an injection site reaction is observed, the subject should be treated at the investigator's discretion. Any adverse reaction (eg, swelling, induration, redness/erythema, pain/tenderness, warmth, bruising or bleeding) should be recorded on the AE page of the CRF. The type of reaction should also be indicated.

Delayed Injection Site, Allergic, and Hypersensitivity Reactions

Reactions following study agent administration may occur 1 to 21 days after study agent injection and presentation can be variable, and can, for example include myalgia and/or arthralgia with fever and/or rash. In some cases, these may be accompanied by other symptoms including pruritus, localized or systemic edema, dysphagia, urticaria, sore throat, and/or headache. Any and all such adverse reactions should be recorded on the AE page of the CRF. The type of reaction should also be indicated.

Self-Assessment

In addition to recording the details of the study agent dosing day, time, anatomic site and if there were any complications of the injection, subjects and/or caregivers should be instructed to monitor the injection site for any reactions, including, but not limited to swelling, redness/erythema, pain, tenderness, warmth, bruising, or bleeding. For severe injection site reactions or changes at the injection site hours to days following injection, the subject/caregiver should contact the study site for consultation.

10. SUBJECT COMPLETION/DISCONTINUATION OF STUDY TREATMENT/ WITHDRAWAL FROM THE STUDY

10.1. Completion

A subject will be considered to have completed the study if he or she has completed assessments at Week 104 of the off-therapy follow-up period or Week 60 of the open-label extension period of the study.

Subjects who prematurely terminate study participation for any reason before completion of the study will not be considered to have completed the study. Subjects are able to initiate the prohibited medicines and activities per the guidance provided in Section 4.3 and Section 8.3.

10.2. Discontinuation of Study Treatment/Withdrawal from the Study

Discontinuation of Study Treatment

A subject will **not** be automatically withdrawn from the study if they have to temporarily or permanently discontinue treatment before the end of the treatment regimen.

If a subject permanently discontinues study treatment for any reason before the end of the treatment phase (Week 52), they should be encouraged to continue with all scheduled visits to and including the final study visit (Week 104), but without receiving study agent administration. If unwilling or unable to participate in all visits, subjects should be encouraged to participate in as many of the planned study visits as possible for continued assessment, but without receiving study agent administration. If the subject is not able to participate in the next 2 sequential study visits that include an MMTT, they should be encouraged to return for the End of Study visits (per the [Time and Events](#) Tables) approximately 10 weeks after their last dose administration.

Similarly, if a subject withdraws following the treatment period (after Week 52) they should be encouraged to participate in the Week 78 and Week 104 visits, as applicable. If the subject is unwilling or unable to complete any of the remaining scheduled study visits, they should be encouraged to return for the End of Study visit (per [Time and Events Schedule](#)) approximately 10 weeks after their last dose administration, as applicable.

Following randomization (ie, between Week 0 and Week 104), consecutive MMTTs should not be repeated if the time interval between them is less than 10 weeks. The MMTT can be repeated in less than 10 weeks only for repeat testing during the screening period or for rescreening.

SAEs will be requested to be submitted for subjects who withdraw early from the study for a year after their last study agent dose (Section [12.4.1](#)).

Subjects who permanently discontinue active treatment during the open-label extension period will have their end-of-study visit followed by the post-treatment visit 10 weeks later.

Study treatment may be temporarily or permanently discontinued due to events described below.

- Events That Result in Permanent Discontinuation of Study Treatment.
 - The investigator believes that for safety reasons or tolerability reasons it is in the best interest of the subject to discontinue study treatment.
 - The subject becomes pregnant.
 - The subject has a severe infection requiring inpatient hospitalization or repeated doses of parenteral antibiotics.
 - The subject has a severe hypersensitivity reaction, such as anaphylaxis or angioedema, to the study agent.
 - The subject has a clinically significant cardiovascular event.
 - The subject is deemed ineligible according to the following TB screening criteria:

-
- A diagnosis of active TB is made.
 - A subject has symptoms suggestive of active TB based on follow-up assessment questions and/or physical examination, or has had recent close contact with a person with active TB, and cannot or will not continue to undergo additional evaluation.
 - A subject undergoing evaluation has a chest radiograph with evidence of current active TB and/or a positive QuantiFERON-TB Gold test result and/or an indeterminate QuantiFERON-TB Gold test result on repeat testing (see Section 9.1.2 and Section 9.1.2.1).
 - The subject misses 3 consecutive study agent administrations.
 - A general lack of compliance with study visits and procedures per study team or sponsor.
 - One confirmed episode of ALT and/or AST $>3x$ upper limit of normal (ULN) as defined in Attachment 5. If a subject has an ALT or AST value of $>3x$ ULN, the next dose of study agent administration should be held pending repeat confirmatory testing which is to take place as soon as possible and preferably within 72 hours. If the value is still $>3x$ ULN then the subject is to permanently discontinue study treatment. If the repeat value is $<2x$ ULN then dosing may proceed. If the repeat value is $\geq 2x$ ULN) and $\leq 3x$ ULN, follow guidelines in the next section.
 - The subject meets criteria for permanent study agent discontinuation based on AST/ALT elevations, AEs, or infections in the next subsection below (Events Resulting In Temporary and Potentially Permanent Discontinuation of Study Agent).
 - Events Resulting in Temporary and Potentially Permanent Discontinuation of Study Treatment.
 - An ALT and/or AST elevation ≥ 2 x the upper limit of normal (ULN) and $\leq 3x$ ULN (as defined in exclusion criteria in Section 4.2.1 and Attachment 5).
 - Repeat AST and ALT as soon as possible but preferably within 72 hours of receipt of the confirmed results. If one or both are ≥ 2 x the ULN and $\leq 3x$ ULN then:
 - Suspend administration of study treatment and recheck the subject within 72 hours and at least weekly as needed thereafter.
 - If AST and ALT are $<2x$ ULN on repeat testing, resume dosing at the next expected interval.
 - If AST and ALT are not $<2x$ ULN by 4 weeks, permanently discontinue study treatment.
- Note: Three independent temporary suspensions from study treatment due to transient elevations in ALT and/or AST $\geq 2x$ but $\leq 3x$ ULN is allowed during the entire treatment period. If a third elevation occurs that requires a dose to be held, permanently discontinue study treatment.
- A Significant Infection.
 - *Defined as:*
 1. Any severe infection meeting SAE criteria as defined in Section 12, or
-

2. Any infection not meeting SAE criteria but otherwise clinically significant per investigator's judgment, *or*
 3. Infection or reactivation of EBV or CMV as defined by clinical signs of infection; or if the EBV viral load is $\geq 10,000$ copies per mL plasma or the CMV viral load is $\geq 10,000$ copies per mL plasma.
- Suspend administration of study treatment and recheck any abnormal laboratory values as soon as possible and preferably within 72 hours.
 - Monitor the subject and abnormal labs at least weekly.
 - If the AE resolves or reduces to mild or less, dosing may resume at the next expected interval.
 - If the AE does not resolve in 4 weeks, permanently discontinue study treatment.
 - A Serious Adverse Event or Study Agent-related Severe Adverse Event.
 - *Defined as:*
 1. Any SAE (as defined in Section 12.1.1) *or*
 2. Any severe AE that is considered related (possibly, probably, or very likely related) to study agent (as defined in Section 12.1.2).
 - With the exception of:

When clinical and laboratory abnormalities are considered related to T1D disease activity (ie, hypoglycemia and hyperglycemia) and study treatment is not considered a contributing factor, administration may not need to be modified. The site investigator should consult with the sponsor if this is encountered.
 - Suspend administration of study treatment and recheck the subject at least weekly; if based on abnormal laboratory values, repeat abnormal laboratory values as soon as possible within 72 hours.
 - If the AE resolves or reduces to a moderate AE (Section 12.1.2) or less, dosing may resume at the next expected interval.
 - If the AE does not resolve to a moderate AE or less (Section 12.1.2) in 4 weeks, discontinue study treatment permanently.

Note: If there are more than 2 suspensions from study treatment due to a specific SAE or related-SAE as defined above, permanently discontinue study treatment.

Withdrawal From The Study

A subject will be withdrawn from the study for any of the following reasons:

- Lost to follow-up.
- Withdrawal of consent/assent.
- Death.

- The study investigator or sponsor, for any reason, decides the subject should be withdrawn from the study.

If a subject is lost to follow-up, every reasonable effort must be made by the study-site personnel to contact the subject and determine the reason for discontinuation/withdrawal. The measures taken to follow-up must be documented.

When a subject withdraws before completing the study, the sponsor and the DMC chair is to be notified and the reason for withdrawal is to be documented in the CRF and in the source document. Study agent assigned to the withdrawn subject may not be assigned to another subject. Subjects who withdraw will not be replaced. If a subject withdraws from the study before the end of study, all attempts should be made to obtain End of Study assessments.

In addition to the above withdrawal criteria, C+R and R responders will be withdrawn if on 2 consecutive occasions 2 months apart, the remission score is >9. The C responders will be discontinued if their remission score is increasing on 2 consecutive occasions by more than 0.5 or if their remission score is 12, whichever comes first.

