4.2.2. Additional Exclusion Criteria for Responders

1. Subjects having reported clinically significant AEs or serious adverse event (SAEs) deemed to be related to the study agent during the double-blind period (e.g. severe infections or hypersensitivity reactions), precluding renewed exposure to golimumab.
2. Subjects who discontinued study agent administration prior to Week 52 or who have completed the Week 104 visit of the double-blind period or discontinued early from the study.
3. Subjects and/or caregivers who are unwilling or unable to administer study agent.

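### The ALT/AST note in Protocol 10.2 allows three temporary suspensions at 2x–3x ULN but orders a permanent stop at the third elevation that requires a held dose

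*Protocol*

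**What the plan says.** Protocol 10.2 sets out what happens when ALT and/or AST is at least 2x and at most 3x ULN and a repeat test confirms it.

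- The action is: "Suspend administration of study treatment and recheck the subject within 72 hours and at least weekly as needed thereafter".
- Dosing restarts once both enzymes are below 2x "ULN on repeat testing, resume dosing at the next expected interval". If they are not below 2x ULN by 4 weeks, treatment stops for good.
- A note then sets the limit on repeat events. Its first sentence allows "Three independent temporary suspensions from study treatment due to transient elevations in ALT and/or AST" in this range over the whole treatment period. Its second sentence says: "If a third elevation occurs that requires a dose to be held, permanently discontinue study treatment".

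The list of permanent-stop events in the same section gives no count of its own for this range. It refers forward: "The subject meets criteria for permanent study agent discontinuation based on AST/ALT elevations, AEs, or infections in the next subsection below". The list does contain one separate rule that matters below: "The subject misses 3 consecutive study agent administrations".

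**The concern.** The two sentences of the note give different answers at the third event. The first makes the third suspension temporary, so dosing may resume when the enzymes fall. The second makes the third elevation permanent if a dose has to be held. Sites acting in good faith can therefore treat the same subject differently.

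This is a liver stopping rule applied at many sites to subjects aged 6 through 21. The choice of reading also feeds into:

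- the discontinuation counts by reason and treatment group (SAP 4.2);
- open-label eligibility, because Protocol 4.2.2 excludes "Subjects who discontinued study agent administration prior to Week 52";
- per-protocol membership as defined in SAP 2.2.1, which requires 52 weeks of treatment to be completed.

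**Working it through.** **Counting the events.** Each confirmed elevation in the range leads to a suspension. Take the k-th one that costs a dose:

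| k | First sentence | Second sentence |
|---|---|---|
| 1 | temporary | temporary |
| 2 | temporary | temporary |
| 3 | temporary | permanent stop |
| 4 | beyond the allowance | already stopped |

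The allowances are 3 and 2. They differ by one, and the conflict is at k = 3.

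**Doses at stake for one affected subject (double-blind period).** Inputs:

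- 27 doses, every 2 weeks from Week 0 to Week 52 (Protocol 7.1.1).
- Chemistry at Weeks 0, 4, 12, 26, 38 and 52 (Time and Events Schedule). If only draws after the first dose count, the third can be no earlier than Week 26.
- Doses lost under the resume reading: at least 1, because the second sentence applies only if a dose is held; at most 2, because three consecutive misses is itself a permanent stop.

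Difference = (doses left after the draw) − (1 or 2 held doses).

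- Third event at Week 26: Weeks 28 to 52 hold 13 doses. 13 − 2 = 11 and 13 − 1 = 12, so 11–12 of 27 (41%–44%).
- Third event at Week 38: Weeks 40 to 52 hold 7 doses. 7 − 2 = 5 and 7 − 1 = 6, so 5–6 of 27 (19%–22%).
- A Week 0 result that comes back from the central laboratory after the first dose could be the first event. The third could then fall at Week 12, with 20 doses left (Weeks 14 to 52): 18–19 of 27 (67%–70%).

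**How often.** The documents give no rate, so the following is assumed: an independent chance p of an elevation that holds a dose at each draw that can still affect dosing. With four such draws (Weeks 4, 12, 26, 38), P(3 or more) = 4p³(1 − p) + p⁴. Adding Week 0 makes five: 10p³(1 − p)² + 5p⁴(1 − p) + p⁵.

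| p | Four draws: P | Expected of 81 | Expected of 54 on golimumab | Five draws: P | Expected of 81 |
|---|---|---|---|---|---|
| 1% | 0.000004 | 0.0003 | 0.0002 | 0.00001 | 0.0008 |
| 5% | 0.00048 | 0.04 | 0.03 | 0.00116 | 0.09 |
| 10% | 0.0037 | 0.30 | 0.20 | 0.00856 | 0.69 |

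The golimumab column matters for open-label eligibility, since only those subjects can enter. Clustering of elevations within subjects, unscheduled tests, and the open-label period (if the note applies there) would raise these figures.

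**The case against.** The best defence is that a suspension and a held dose are different things. Dosing is every 2 weeks and the recheck is within 72 hours, so a suspension can open and close between doses. The first sentence would then allow three suspensions, and the second would end treatment only if the third costs a dose. A site facing a third held dose would also have just one direct order, which is to stop.

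Part of this stands: if the third suspension costs no dose, there is no conflict. That is why the dose ranges above subtract at least one held dose; 13 and 7 would be too high as upper ends. But the defence does not remove the problem. Neither term is defined. Section 10.2 also uses a held dose for the pause after a value above 3x ULN, and if the repeat falls between 2x and 3x it sends that subject into the suspension pathway, so the terms overlap. When the third event does cost a dose, the first sentence still counts that suspension among those allowed.

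Two further objections stand in full.

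- The hepatic risk is limited under either reading. A confirmed value above 3x ULN, failure to fall below 2x by 4 weeks, and three consecutive missed doses are each permanent stops, and the investigator may stop treatment for safety. A reader might infer that the note leaves subjects without an effective liver stopping rule; these provisions show otherwise.
- The per-protocol effect depends on which definition is used. SAP 5.3.2.2 (sensitivity analysis 1) removes only subjects with major deviations identified from a blinded list and does not require 52 weeks of treatment. Stopping as the protocol directs would not by itself exclude anyone there.

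**Conclusion.** The inconsistency is real and nothing else in the protocol or SAP resolves it. It is minor. For an affected subject it is worth 11–12 of 27 doses from Week 26 or 5–6 of 27 from Week 38, and more if a Week 0 result brings the third event to Week 12. Fewer than one subject is expected to reach it at the assumed 1% to 10% per draw, with independent draws in the double-blind period.

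It bears on site safety conduct, discontinuation counts, open-label eligibility for golimumab responders, and per-protocol membership under SAP 2.2.1 but not under SAP 5.3.2.2.

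Two stronger inferences are not supported. A reader might infer that the primary result is at risk, but anyone who took at least one dose stays in the full analysis set, and the primary model, sample size and power do not depend on this count. A reader might also infer that two suspensions were clearly intended, because the neighbouring SAE rule orders a permanent stop in these terms: "If there are more than 2 suspensions from study treatment due to a specific SAE or related-SAE as defined above". That fits a limit of two but does not prove it, since that rule counts suspensions for a specific SAE.

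**What to change.** In the ALT/AST note of Protocol 10.2, replace *Three* with *Two* in the first sentence and leave the third dose-holding elevation as a permanent stop. This is the cautious reading, and the sponsor should confirm it. If three suspensions were intended, keep *Three* and change *third* to *fourth* in the second sentence. Either way, use one term, suspension or held dose, in both sentences.

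The cost is wording only, by amendment or a clarification letter to sites, with no new data or procedures. The downside of *Two* is that a few subjects may stop who could have resumed, and any golimumab responders among them would lose access to the open-label extension.

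### Protocol Section 10.2: a serious infection graded moderate or mild misses the infection dosing rule and falls under the looser general SAE rule

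*Protocol*

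**What the plan says.** Protocol Section 10.2 lists events that lead to temporary and possibly permanent discontinuation. Two of its rules matter here.

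**Significant Infection.** Item 1 is "Any severe infection meeting SAE criteria as defined in Section 12". Item 2 is "Any infection not meeting SAE criteria but otherwise clinically significant per" the investigator's judgment. Item 3 is EBV or CMV infection or reactivation, whatever its grade. Treatment is suspended and the subject is monitored at least weekly. Then: "If the AE resolves or reduces to mild or less, dosing may resume at the next expected interval", and "If the AE does not resolve in 4 weeks, permanently discontinue study treatment".

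**SAE or study agent-related severe AE.** Item 1 is any SAE. Item 2 is "Any severe AE that is considered related (possibly, probably, or very likely related) to study agent". The instruction is "Suspend administration of study treatment and recheck the subject at least weekly". Then: "If the AE resolves or reduces to a moderate AE (Section 12.1.2) or less, dosing may resume at the next expected interval", and "If the AE does not resolve to a moderate AE or less (Section 12.1.2) in 4 weeks, discontinue study treatment permanently". The only written exception is for T1D disease activity; infections are not carved out.

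The list of permanent-stop events in the same section has an infection bullet, but it too is limited to severe infections (those needing admission or repeated parenteral antibiotics). Active TB is a permanent stop at any severity. Section 12.1.1 defines seriousness, and admission alone is enough. Section 12.1.2 defines mild, moderate and severe separately, by discomfort and function.

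**The concern.** Items 1 and 2 look as though they were meant to split infections into serious and non-serious. The word severe in item 1 breaks that split, because a serious infection need not be graded severe. Those left out drop to a rule written for SAEs in general, whose threshold for redosing is one grade higher.

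Serious infection is a named class risk of TNF-alpha blockers in Section 1.1, which also says that a significant share of the target population is under 18. At stake are subject safety and consistent practice between sites when deciding whether to redose after an infection.

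**Working it through.** The plan states no figure on this point, so the check is to run each type of infection through the rules. All rows exclude EBV/CMV (item 3) and active TB (permanent stop).

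| Infection | Permanent-stop infection bullet | Item 1 | Item 2 | SAE rule | Resume at | 4-week stop |
|---|---|---|---|---|---|---|
| Moderate, SAE | No, not severe | No, not severe | No, is an SAE | Yes | Moderate or less | Only above moderate |
| Mild, SAE | No, not severe | No, not severe | No, is an SAE | Yes | Moderate or less | Only above moderate |
| Moderate, not SAE, judged clinically significant | No, not severe | No, not an SAE | Yes | No | Mild or less | If not resolved |

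Comparing rows 1 and 3, the grade is the same, yet the serious event has the higher resumption threshold and the narrower 4-week stop. In row 2 the event is already mild, so either rule would allow resumption; only the 4-week stop differs.

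Next, what this means for an infection that stays moderate for 4 weeks. Dosing is every 14 days, so the window holds 28/14 = 2 dosing intervals.

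- **Non-serious, clinically significant:** no doses, and a permanent stop at 4 weeks.
- **Serious, permissive reading** (an event that began at moderate already counts as moderate or less): up to 2 doses, and no 4-week stop.
- **Serious, conservative reading** (the event must come down from where it started): no doses. The SAE rule's own 4-week stop is not triggered, but Section 10.2 also makes 3 consecutive missed administrations a permanent stop and does not exempt mandated holds. If the first held dose falls d days after onset, with d from 0 to 14, the third is missed on day d + 28, that is, day 28 to day 42. The stop then comes 0 to 14 days later than under the infection rule.

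With severe deleted from item 1, rows 1 and 2 answer yes to item 1. Dosing may then resume only at mild or less, with a permanent stop if the infection is unresolved at 4 weeks. This matches row 3.

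**The case against.** The strongest reply is that this is loose wording inside a well-guarded process. Suspension is mandatory for every SAE, with rechecks at least weekly. The investigator may stop treatment on safety grounds (Section 10.2), and dosing is held during a febrile episode (Section 6.2). SAEs go to the sponsor within 24 hours (Section 12.4.2) and to the unblinded DMC on an ongoing basis (Section 9.6). These controls limit the harm, and that part of the reply stands. They do not give the moderate serious infection the explicit threshold that the protocol writes for non-serious ones.

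It can also be said that severe was meant as serious. There is some support: Section 4.2.2 uses severe infections as an example of excluding AEs or SAEs, and the Note closing the SAE rule writes related-SAE where the definition says related severe AE. But Section 12 keeps the two scales apart, and the SAE rule's own title names both. A site that reads item 1 literally reads it correctly. Whatever was intended, the same edit settles it.

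Two stronger readings are not supported.

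- A reader might infer that the plan lets two doses be given to a subject with a persistently moderate serious infection, with no stop. That needs the permissive reading, which is weak: it would leave the mandatory suspension of a moderate SAE without effect, and wording about resolving or reducing implies improvement.
- A reader might infer that the overlap of rules for severe serious infections, or for EBV/CMV SAEs, is a contradiction needing a ranking sentence. It is not. Resumption is worded as a permission, so one rule's permission does not cancel another's hold, and applying the strictest satisfies them all. A sentence ranking permanent discontinuation first could also force out a subject who resumed at mild but is not fully resolved at week 4.

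**Conclusion.** The point holds as a gap in a dosing-safety rule. Outside EBV/CMV and active TB, a serious infection graded moderate or mild is governed by the general SAE rule alone, and its written threshold is looser than that for a clinically significant non-serious infection.

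The practical effect is small. The documents give no event rate for this trial, and Section 1.1 describes the class risks as having very low frequency, so few subjects would be affected. The comparison assumes that the investigator judges the non-serious infection clinically significant. The 3-missed-doses backstop assumes that held doses count as missed. Nothing here bears on sample size, power or the primary analysis. The correction is nonetheless worth making, because it concerns a named safety risk and costs almost nothing.

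**What to change.** Delete the word severe from item 1 of the Significant Infection definition in Section 10.2, so that the item covers every infection meeting the SAE criteria. Items 1 and 2 then divide infections cleanly by seriousness.

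Leave the SAE rule as it is, still applying to infections. Its item 2 is what requires a hold for a severe, study agent-related, non-serious infection whether or not it is judged clinically significant, and its Note caps repeated suspensions.

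The cost is one word in an amendment. A few subjects may be held longer or stopped, including some mild serious infections not fully resolved at 4 weeks. Visits, sample size and analyses do not change.
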